## **Study Protocol:**

### **Background**

Parkinson's disease (PD) is a complex neurological disease that affects ~6.1 million people worldwide – mostly older adults  $\geq 60$  years. The most effective treatment for PD is dopaminergic therapy, particularly levodopa (Ldopa). People with PD have variable responses to Ldopa, including degrees of motor fluctuations (MF) throughout the day. The half-life of Ldopa is ~1.5 h and therefore, dosage and timing are essential to mitigate MF. Ldopa is a large neutral amino acid (LNAA), and the bioavailability of Ldopa is compromised when simultaneously ingested with LNAA (e.g., leucine). Both Ldopa and LNAs from food are absorbed through the same intestinal transporter, but LNAs from food are preferentially absorbed by the enterocyte, limiting the bioavailability of Ldopa. Thus, the scientific community often recommends the protein-redistribution diet (PRD). With PRD, patients limit protein (<10 g) at the desired time of medication efficacy (daytime) and meet their protein needs during the evening meal (~70+g). There are deleterious implications of the PRD for older adults with PD; consumption of >30 g of protein, in a single meal, will not sufficiently increase muscle protein synthesis. Additionally, the impact of the PRD on skeletal muscle quality and function has not been determined, and it is unclear, based on prior studies, whether the PRD enhanced drug absorption.

### **Objectives**

Our overarching objective is to generate preliminary data on the impact of the dietary protein pattern on markers of skeletal muscle health and drug efficacy in PD. This objective will be met with the following **Aim 1**. Quantify the effects of dietary protein pattern on skeletal muscle in Parkinson's Disease (PD). We will assess changes in (i) circulating biomarkers associated with muscle catabolism (serum GDF15 and FGF21) and (ii) muscle strength (handgrip dynamometry). **Aim 2**. Determine the effects of dietary protein pattern on sleep quality in PD. PD symptoms, including sleep, will be assessed via actigraphy.

This was a 5-week randomized crossover pilot study with n=12 participants with PD. Participants were recruited through the UAB Comprehensive Parkinson Disease and Movement Disorders Clinic, Tanner Foundation, Lakeshore Foundation, Parkinson Association of Alabama, and local PD support groups. Eligibility to participate: diagnosed with PD for  $\geq 5$  years,  $\geq 45$  years of age, on a stable Ldopa regimen, self-reported motor fluctuations, and no dietary restrictions that would preclude participation in this study. Eligible participants were randomized to follow a PCD (20-30g protein per meal) or a PRD ( $\leq 10$ g until evening meal) for 2 weeks, complete a 1-week washout period, and then follow the other respective diet for the remaining 2 weeks (Figure 1). Participants received one-on-one education and supportive materials on how to follow their assigned diets. Participants were instructed to take their medications 30 minutes before or 2 hours after a meal. As nausea is a common side effect for Ldopa medications, they were given a list of snack options without protein to take with their medication. Outcome measures will be assessed at weeks 0, 2 (day 14), 3 (day 21), and 5 (day 35) at Lakeshore campus.

Feasibility measures will be assessed throughout the study, including diet adherence (food records); process evaluations of study visits; time to reach recruitment goal; attrition rate; and acceptability date from exit interviews. Outcome measures, including serum GDF15 and FGF21,

handgrip dynamometry, sleep actigraphy, Parkinson's symptoms (MDS-UPDRS), and physical activity (actigraphy) will be assessed at weeks 0, 2, 3, and 5.

Statistical analysis:

This is a pilot and feasibility study that was intended to generate power and sample size calculations for a subsequent study. Outcome measures for this acute study are continuous variables that will be compared within group (paired t-test) and between groups (independent t-test)

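### Aim 1 leaves its changes and the PCD-PRD contrast undefined; if period baselines are subtracted, a paired contrast may have up to about twice the variance of end-of-diet values

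*Combined protocol and SAP*

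**What the plan says.** The Objectives section describes the design: "This was a 5-week randomized crossover pilot study with n=12 participants with PD". Participants follow one diet "for 2 weeks, complete a 1-week washout period, and then follow the other respective diet for the remaining 2 weeks". On timing it says "Outcome measures will be assessed at weeks 0, 2 (day 14), 3 (day 21), and 5 (day 35) at Lakeshore campus", so weeks 0 and 3 open the two diet periods and weeks 2 and 5 close them.

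For Aim 1 it says "We will assess changes in (i) circulating biomarkers associated with muscle catabolism (serum GDF15 and FGF21) and (ii) muscle strength (handgrip dynamometry". It does not say what the change is measured from.

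The statistical analysis paragraph says "Outcome measures for this acute study are continuous variables that will be compared within group (paired t-test) and between groups (independent t-test". It does not define group, does not say whether the analysed variable is an end value or a change, and does not mention the period baselines. It gives the purpose as follows: "This is a pilot and feasibility study that was intended to generate power and sample size calculations for a subsequent study". No SD, correlation, alpha, power or target difference is stated.

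**The concern.** A fresh measurement at week 3, after the washout, together with an aim framed as change, points to (week 2 − week 0) compared with (week 5 − week 3). In a crossover, a stable person effect already cancels when the two diets are compared within a person. Subtracting two baselines then removes no more of that effect and adds the error of two further visits. This loss of precision would arise even if the washout were complete, so it is separate from carry-over.

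Two things are at stake: the precision available from 12 people, and the SD carried into the sample size of the next study.

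**Working it through.** There is no figure in the plan to reproduce. The inputs taken from it are the four visits (weeks 0, 2, 3, 5), two diets in two periods, and n=12. All correlations, the power and the alpha below are assumptions.

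**Contrasts on visits (0, 2, 3, 5).** End-of-diet: (0, 1, 0, −1). Difference of changes: (−1, 1, 1, −1). Variances are in units of the single-visit variance.

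**(a) Equal correlation r between all visits.** End values: 2(1−r). Changes: 4(1−r). The ratio is 2.00 for every r, and the SE ratio is √2 = 1.41.

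**(b) Serial correlation r per week.** End values: 2 − 2r³. Changes: 4 + 2(r − 2r² − 2r³ + r⁵).

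| r | Changes | End values | Ratio |
|---|---|---|---|
| 0.3 | 4.137 | 1.946 | 2.13 |
| 0.5 | 3.562 | 1.750 | 2.04 |
| 0.7 | 2.404 | 1.314 | 1.83 |
| 0.8 | 1.647 | 0.976 | 1.69 |
| 0.9 | 0.825 | 0.542 | 1.52 |
| 0.99 | 0.080 | 0.059 | 1.35 |

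As r approaches 1 the ratio tends to 4/3, so the penalty never disappears under this structure.

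**(c) Correlation rw within a period and rb between periods.** End values: 2(1−rb). Changes: 4(1−rw). Ratio: 2(1−rw)/(1−rb).

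| rw / rb | Ratio |
|---|---|
| 0.9 / 0.9 | 2.00 |
| 0.8 / 0.7 | 1.33 |
| 0.7 / 0.5 | 1.20 |
| 0.9 / 0.8 | 1.00 |
| 0.9 / 0.7 | 0.67 |

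**Baseline difference as a covariate.** Under (a), the covariance of (Y2 − Y5) with (Y0 − Y3) is r − r − r + r = 0, so the covariate gets no weight and the end-value variance is kept. Under (c) its coefficient is b = (rw−rb)/(1−rb) and the residual variance is 2(1−rb)(1−b²). At 0.9/0.7, b = 0.2/0.3 and the variance is 0.6 × (1 − 4/9) = 0.33, against 0.4 for changes and 0.6 for end values. At 0.9/0.8, b = 0.5 and it is 0.4 × 0.75 = 0.30, against 0.4 for both. Apart from the cost of estimating b, the covariate does no worse than either fixed choice.

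**Detectable difference.** Assume a paired analysis, independent visit errors with SD sw, 80% power and two-sided 5%. The detectable standardised paired difference at n=12 is 0.889. Changes: 0.889 × 2sw = 1.78 sw. End values: 0.889 × 1.414sw = 1.26 sw.

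**If the diets are compared by an independent t-test.** Under equal correlation, the variance that test uses is 2 for end values and 4(1−r) for changes, a ratio of 2(1−r): 1.0 at r=0.5 and 0.4 at r=0.8. The true variance of the end-value difference is still 2(1−r), so its SE is overstated by 1/√(1−r), which is 2.24 times at r=0.8.

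**The case against.** The strongest reply is that the plan never specifies the analysis being priced. The change could be from period start, from week 0 in both periods, or simply a difference between diets. A reader might infer that Aim 1 commits to change from period start; the visit schedule suggests it, but no sentence says so. This part of the objection stands, and the point is therefore conditional.

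Second, the paragraph names an independent t-test between groups. If that test compares the diets, changes give the smaller nominal variance once r exceeds 0.5. This also stands, but it is a property of an SE that ignores the pairing. The sampling variance of the estimated diet difference still follows the contrasts above. The practical consequence is that moving to end values while keeping the unpaired test would make matters worse.

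Third, the doubling depends on the correlation structure. Parity or reversal requires visits two weeks apart in the same period, with a diet change between them, to correlate well above visits across periods. Nothing in the documents suggests such a large person-by-period shift, and nothing rules it out.

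Finally, a reader might infer that change scores leave 12 people worth 6, or that the SD passed on will be about 40% too large. Both are the factor of 2 restated, so they need equal correlation. The second also needs to know which SD will be used and what design comes next, and the plan gives neither. All four visits are collected, so every version of the SD remains computable.

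**Conclusion.** The point holds in conditional form. The plan does not define the PCD-PRD contrast for Aim 1. If the contrast is the difference of changes from period start and is analysed within person, its variance is 2.00 times that of the end-of-diet contrast under equal correlation and about 1.3 to 2.1 times under serial correlation. It could equal the end-of-diet variance or fall below it if within-period correlation is strong. The detectable differences apply only under the paired, independent-error, 80% power and 5% alpha assumptions, and they contradict nothing in the plan, which states none of these. This is a worthwhile improvement in precision and clarity; it does not show that the planned analysis is invalid.

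**What to change.** For the Aim 1 outcomes (GDF15, FGF21, handgrip), define the diet effect as the within-person PCD-PRD difference between the end-of-diet values at weeks 2 and 5, adjusted for period. Enter the within-person difference between the period baselines (weeks 0 and 3) as a covariate. State that this replaces the independent t-test between diets, and adopt both parts together. Report before-after changes within each diet descriptively. Give the SD of the adjusted within-person contrast for planning the next study.

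The cost is about one degree of freedom for period and one for the covariate: from 11 for a simple paired comparison of 12 people to about 9. No new data are needed. The Objectives section mixes past and future tense, so if data have already been seen, the change must be disclosed as post hoc.

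### Before-after change on each diet depends on participants' habitual diet, which the plan does not say it records; diet conclusions should rest on the paired end-of-period PCD-PRD contrast

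*Combined protocol and SAP*

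**What the plan says.** The Objectives section describes the design: "This was a 5-week randomized crossover pilot study with n=12 participants with PD". Participants follow PCD or PRD for 2 weeks, then "complete a 1-week washout period, and then follow the other respective diet for the remaining 2 weeks". What is eaten during washout is not stated.

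Eligible people have had PD for at least 5 years and are "on a stable Ldopa regimen, self-reported motor fluctuations". The only dietary criterion is "no dietary restrictions that would preclude participation in this study"; it does not mention PRD. The Background observes that "the scientific community often recommends the protein-redistribution diet (PRD"), without saying how many patients follow that advice.

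Aim 1 is framed as changes in biomarkers and grip strength. Visits bracket each diet period: "Outcome measures will be assessed at weeks 0, 2 (day 14), 3 (day 21), and 5 (day 35"). Food records are listed as the adherence measure among the feasibility outcomes. No pre-study diet record, run-in or stratification by habitual protein pattern is described.

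Under Statistical analysis, outcomes are to be "compared within group (paired t-test") and compared between groups by an independent t-test. Neither comparison is defined further. The same section says the study is meant to supply inputs for sizing a later trial.

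**The concern.** If the paired test compares the start and end of each diet period, its reference is whatever the participant was eating at week 0 or week 3. Nothing in the plan fixes or measures that. People with long-standing PD and motor fluctuations on Ldopa, recruited partly through a movement disorders clinic and support groups, are plausible recipients of PRD advice, and someone already following PRD could still follow both study diets. For that person the PRD period brings no change of diet, and the PCD period carries the whole contrast.

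At stake is interpretation. Two separate before-after tests could show one diet moving an outcome and the other not, when that split reflects where participants started. A within-diet change or its SD, carried into the later trial's sample size, would inherit the same dependence. Adherence and acceptability could also partly reflect familiarity with one diet, though the documents give nothing from which to size that.

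**Working it through.** The plan gives no power calculation, effect size, SD or alpha, so there is no figure to reproduce.

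**Inputs.** From the documents: n = 12, crossover, outcomes at weeks 0, 2, 3 and 5. Assumed: two-sided alpha 0.05; SD of a within-person change = 1; washout returns each person to the habitual diet; D = 0.889 SD, the difference that a paired t-test on 12 detects with 80% power (noncentrality 0.889 × √12 = 3.08, 11 df).

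**Expected changes.** Set the outcome level at 0 on PRD, D on PCD and H on a habitual non-PRD diet. Let a share f enter already on PRD.

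- Change on PRD = −(1−f)H
- Change on PCD = (1−f)(D−H) + fD = D − (1−f)H
- Difference of the two changes = D, for every f and H

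**Case 1: other participants eat at the PCD level (H = D = 0.889).** The changes become −(1−f)D and fD. Rejection rates are from 60,000 simulated trials of 12.

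| PRD eaters of 12 | PRD change | PCD change | PRD test significant | PCD test significant |
|---|---|---|---|---|
| 0 | −0.889 | 0 | 80% | 5% |
| 3 | −0.75 × 0.889 = −0.667 | 0.222 | 50% | about 9% |
| 6 | −0.444 | 0.444 | 23% | 23% |
| 9 | −0.222 | 0.667 | about 8% | 50% |

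The model is symmetric, so the entries of about 8% and 9% estimate the same rate; they differ only by simulation error. With independent errors in the two changes, 76% of trials with no PRD eaters show PRD significant and PCD not. With 9 PRD eaters, 46% show the opposite.

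**Case 2: habitual diet midway (H = 0.5, D = 1; noncentral t with change variance 1 + f(1−f)H²).** D differs from Case 1, so compare the pattern and not the levels.

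| PRD eaters of 12 | PRD change | PCD change | PRD power | PCD power |
|---|---|---|---|---|
| 0 | −0.50 | 0.50 | 0.35 | 0.35 |
| 6 | −0.25 | 0.75 | 0.12 | 0.63 |
| 12 | 0 | 1.00 | 0.05 | 0.88 |

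**No true difference.** If D = 0 and H = 0, both changes are zero at every f and each test rejects in about 5% of trials.

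**Paired end-of-period contrast.** Its expectation is D at every f and H. If its SD is also 1, power is 80% at D = 0.889 and 88% at D = 1, whatever the mix.

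**Carry-forward.** With 6 PRD eaters in Case 1, each within-diet change is half of D. Because required sample size varies as 1/effect², that alone would multiply a later sample size by about 1/0.5² = 4. The SD of change also rises, to √(1 + 0.25 × 0.889²) = 1.09.

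**Chance that anyone is affected.** If 5%, 10%, 20% or 30% of eligible people already eat a PRD (assumed), 1 − (1−p)^12 gives a 46%, 72%, 93% or 99% chance of at least one among 12.

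**The case against.** Several objections have force.

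- A reader might infer that enrolling PRD users is the cause and excluding them the cure. The arithmetic says otherwise: in Case 1 the split is most one-sided when nobody eats a PRD (80% against 5%) and vanishes at 6 of 12. The fault lies in judging diets by separate before-after tests, whatever people habitually eat.
- A reader might infer that the mix can manufacture a diet effect. It cannot; with D = 0 neither test rejects beyond its nominal rate.
- The before-after reading is likely but not explicit. A within-group paired test in a crossover could mean PCD against PRD within participants, which is immune to this problem. The plan does not say which it intends, and its only between-group test is an independent one.
- The premise is inference. PRD being recommended does not mean it is followed, no prevalence is given, and the dietary criterion could be applied so as to exclude current PRD users. It could equally admit them.
- The Case 1 pattern depends on placing all other participants exactly at the PCD level, and D is not a document figure. Case 2 gives equal changes at zero PRD eaters, so the direction of imbalance is not predictable from the plan.
- Feasibility measures are to be assessed throughout, so food records at week 0 or in washout cannot be ruled out.

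What survives is that, in both cases, the split of D between the two changes moves with a quantity that the plan does not say it records.

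**Conclusion.** The concern holds in limited form. On the most natural reading of the planned paired test, each before-after result depends on participants' habitual diet. In the illustration, the chance of significance ranges from about 80% down to 8% for PRD, and from 5% up to 50% for PCD, with the same true difference throughout. These figures rest on assumed values for D, the SD, alpha, the habitual non-PRD level and the number of PRD eaters; the documents supply only n = 12 and the visit schedule.

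The documents do not support saying that the randomised PCD-PRD comparison within participants is biased by habitual diet, that PRD users were in fact enrolled, or that washout is a return to PRD, since the washout diet is unspecified. The stability of the end-of-period contrast in turn assumes no carry-over from the first diet into the second end-of-period visit. For a pilot meant to inform a later trial, the change is worthwhile because it costs little and protects the estimates to be carried forward.

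**What to change.** In the Statistical analysis section, define the diet comparison as the within-participant (paired) difference between the end-of-PCD and end-of-PRD values. Base diet conclusions on it, and take from it any effect size or SD used to size the later study. Report within-diet changes descriptively, without significance tests.

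Where still possible, take one food record at week 0 before diet education and one during washout, and describe habitual protein pattern alongside adherence and acceptability. Do not test subgroups by habitual pattern; 12 people cannot support it. Parts of the protocol are in the past tense, so if the data are already collected, use whatever existing records show about usual diet, or state the limitation and build the records into the subsequent study.

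Cost: a change of SAP wording, at most two extra food records per participant and no extra visit. The downside is that within-diet p-values are no longer available as findings.

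### If the medication-meal timing instruction began after week 0, a before-after test within each diet cannot separate it from the diet; the randomized between-diet contrast can

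*Combined protocol and SAP*

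**What the plan says.** The Objectives section describes the design: "This was a 5-week randomized crossover pilot study with n=12 participants with PD". Participants follow one diet "for 2 weeks, complete a 1-week washout period, and then follow the other respective diet for the remaining 2 weeks". On visits it says: "Outcome measures will be assessed at weeks 0, 2 (day 14), 3 (day 21), and 5 (day 35) at Lakeshore campus".

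Directly after the randomization sentence come three measures:

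- diet education: "Participants received one-on-one education and supportive materials on how to follow their assigned diets";
- a timing rule: "Participants were instructed to take their medications 30 minutes before or 2 hours after a meal";
- a snack list: "they were given a list of snack options without protein to take with their medication".

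The timing rule and snack list are stated once, for all participants. The text gives no start date for them, mentions no run-in, and does not say whether they applied in the washout week. Entry requires a stable levodopa regimen but sets no condition on how doses were previously timed around meals.

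The Statistical analysis paragraph says that continuous outcomes are to be "compared within group (paired t-test") and between groups by independent t-test. Group is not defined. The same paragraph gives the study's purpose as producing power and sample size calculations for a later study.

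**The concern.** The Background says of levodopa that "dosage and timing are essential to mitigate MF", and that large neutral amino acids taken at the same time reduce its bioavailability. By that reasoning, separating doses from meals could change Parkinson's symptoms under either diet, whatever the protein pattern.

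If the rule came into force between weeks 0 and 2, the week-2 measurement reflects diet plus new timing, while week 0 reflects whatever the participant did before. A before-after paired test assigns the whole change to the diet, together with any other effect of time or repeated visits. Both diets could then appear to help when neither did.

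Because the pilot exists to size a later trial, a within-diet effect size carried into that calculation would include the timing effect.

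**Working it through.** The plan states no power, alpha, effect size or SD, so there is no figure to reproduce. The check asks how often a before-after test would reject if the diet did nothing.

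**Inputs from the Objectives section.** n=12; two diet periods; assessments before and after each (weeks 0 and 2, weeks 3 and 5).

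**Assumptions.** True diet effect 0; two-sided 5% test; change scores with SD 1, independent across periods; 6 participants per sequence; an additive timing effect of d SD of the change score. The value of d is not in the documents, so a range is shown.

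**Case A: every participant's change is shifted by d.** This happens if the timing effect restarts in each period, or if it persists and week 0 is the baseline for both diets. Bias is d. The paired t statistic has 12 − 1 = 11 degrees of freedom and noncentrality d√12:

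- d=0.3: 0.3 × 3.464 = 1.04, rejection 16%
- d=0.5: 0.5 × 3.464 = 1.73, rejection 35%
- d=0.8: 0.8 × 3.464 = 2.77, rejection 71%

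**Case B: the effect persists through washout, and each period uses its own baseline.** Week 3 already contains the effect, so only period-1 changes are shifted. Each diet is taken in period 1 by 6 of 12 participants, so the bias is (6 × d + 6 × 0)/12 = d/2. Rejection comes from simulation (40,000 runs).

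| d | Case A, per diet | Case A, at least one diet* | Case B, per diet | Case B, at least one diet |
|---|---|---|---|---|
| 0 | 5% | 10% | 5% | 9% |
| 0.3 | 16% | 29% | 7% | 14% |
| 0.5 | 35% | 58% | 11% | 21% |
| 0.8 | 71% | 92% | 20% | 36% |

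*Simulated for the restart version, in which the two diets have separate baselines.

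**Between-diet contrast.** In Case A with restart, d enters both diets' changes and cancels: simulated bias is about 0 and rejection about 5%. In Case B, the within-person difference of changes is shifted by +d in one sequence and −d in the other, which averages to zero with 6 and 6. Bias is again about 0, but the spread grows. The expected sample variance of the differences rises from 1 + 1 = 2 to 2 + 12d²/11:

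- d=0.5: 2 + 12 × 0.25/11 = 2.27, so the SD is inflated by √(2.27/2) = 1.07
- d=0.8: 2 + 12 × 0.64/11 = 2.70, so the SD is inflated by √(2.70/2) = 1.16

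This agrees with the simulated paired rejection rates of 3.8% and 2.6%, below 5%. A standardized effect from that contrast, without a period term, would be too small by the same factors. Comparing week 2 with week 5 directly avoids this when the effect persists, because both measurements contain it.

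**The case against.** The strongest reply is that much of this rests on silence. The text does not say when the timing rule began, how participants timed doses before entry, or what applied in washout. The schedule refers to a figure that is not reproduced in the text available, and it might answer some of this. This stands: the onset after week 0 is a condition of the point, not a fact.

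Second, in a crossover a paired test could equally mean the within-person comparison of the two diets, to which the criticism does not apply. This also stands. The before-after reading is favored because the aim speaks of assessing changes and the visits bracket each diet period, but it is an inference.

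Third, the aims concern dietary protein pattern, and giving everyone the same timing rule is a reasonable way to standardize. A reader might infer that the comparison of the two diets is confounded. The documents do not support that: the rule is common to both diets, and the randomized contrast removes an additive effect. It would not remove an interaction between diet and timing.

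Fourth, a reader might count the one-on-one education as a further confounder. It is education in following the assigned diet, so it is part of how the diet is delivered. The separable co-intervention is the timing rule with its snack list.

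Fifth, the Background's mechanism concerns levodopa absorption and motor fluctuations. It does not extend to grip strength or sleep, and nothing there links dose timing to GDF15 or FGF21. The point is strongest for Parkinson's symptoms and weaker for the Aim 1 biomarkers.

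**Conclusion.** The point holds conditionally. If the timing rule and snack list began after week 0, and if the paired test is before-after within each diet, a significant result cannot be attributed to the diet. With no diet effect and n=12, the per-diet rejection rate is 7% to 20% for d from 0.3 to 0.8 if the effect persists through washout with period-specific baselines. It is 16% to 71% if the effect restarts or week 0 serves both diets. The higher range should not be read as the expected case: the plan schedules a week-3 assessment just before period 2, and d is an assumption throughout.

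A reader might also infer that within-diet effect sizes are destined for the next trial's sample size. The plan does not say which contrast will be used; the risk is that nothing rules this one out.

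This is a matter of analysis definition and reporting. It does not undermine the randomized comparison, and it takes no view on the medication timing rule itself.

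**What to change.** Leave the timing instruction and snack list as they are, and change the analysis text:

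1. Define the diet effect as the within-person contrast of the protein-redistribution diet (PRD) with its comparator (PCD) at the end-of-diet assessments (weeks 2 and 5), with a period term.
2. State that effect sizes and variances for the next study come from that contrast.
3. Report within-diet before-after changes descriptively, without tests presented as diet effects.
4. State when the timing instruction and snack list were given relative to week 0, and whether they continued through washout.

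The cost is wording, the loss of two uncontrolled within-diet claims, and one degree of freedom for period (from 12 − 1 = 11 to 12 − 2 = 10). Giving the instruction before week 0 would also have worked, but the design is described largely in the past tense, so that option is probably closed.

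### The independent t-test between groups ignores the crossover pairing if it compares the diets on end values, and the plan does not specify the within-person diet contrast

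*Combined protocol and SAP*

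**What the plan says.** The Objectives section describes the design: "This was a 5-week randomized crossover pilot study with n=12 participants with PD". Participants take one diet for 2 weeks, "complete a 1-week washout period, and then follow the other respective diet for the remaining 2 weeks". Outcomes are measured at weeks 0, 2, 3 and 5, so each diet period has its own start and end visit.

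Both aims are about the diets. Aim 1 is to "Quantify the effects of dietary protein pattern on skeletal muscle" and adds "We will assess changes in (i) circulating biomarkers associated with muscle catabolism". Aim 2 is to "Determine the effects of dietary protein pattern on sleep quality in PD".

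The Statistical analysis paragraph gives the purpose, "This is a pilot and feasibility study that was intended to generate power and sample size calculations for a subsequent study", and then the whole method: continuous outcomes are to be "compared within group (paired t-test) and between groups (independent t-test". It does not say whether a group is a diet or a randomized sequence, whether end values or changes are compared, or what the paired test pairs. It names no period term.

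**The concern.** The design section contrasts only the two diets and never speaks of sequences. The natural reading is therefore a before-and-after paired test within each diet and an independent test of one diet against the other. The two diet arms contain the same 12 people, so the independence assumption fails, and on end values the main gain from a crossover is lost.

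Two things are at stake. The diet effect would be reported with intervals wider than the design earns, and a real difference could be missed. The pilot might also fail to report the SD of the within-person diet difference, although supplying sample-size inputs is its stated purpose. A before-and-after paired test does not fill that gap: it gives the SD of change on one diet, which is a different quantity.

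**Working it through.** **Inputs.** From the Objectives section: 12 participants, both diets in each, visits at weeks 0, 2, 3 and 5. The plan states no power, SD, effect size or significance level, so there is no figure to reproduce. Assumed: two-sided 5%, six per sequence, no dropout, normal data, a common SD of 1, and a range of ρ.

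**Reading 1: diets compared on end values (week 2 and week 5).**
- True variance of the mean difference: 2(1−ρ)/12. The independent test works with 2/12. The ratio is 1/(1−ρ): 2.0, 3.3 and 5.0 at ρ = 0.5, 0.7 and 0.8.
- Independent half-width: t(22) × √(2/12) = 2.074 × 0.408 = 0.847, whatever ρ is.
- Period-adjusted half-width: t(10) × √(2(1−ρ)/12), with t(10) = 2.228.
- Break-even: ρ = 1 − (2.074/2.228)² = 0.13.

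Type I error and power below are simulated (200,000 or more trials per ρ).

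| ρ | Independent half-width | Period-adjusted half-width | Ratio | Type I error, independent | Power for 0.5 SD: independent / paired |
|---|---|---|---|---|---|
| 0.1 | 0.847 | 0.863 | 0.98 | 4.0% | 21% / 22% |
| 0.3 | 0.847 | 0.761 | 1.11 | 2.1% | 18% / 27% |
| 0.5 | 0.847 | 0.643 | 1.32 | 0.9% | 15% / 35% |
| 0.7 | 0.847 | 0.498 | 1.70 | 0.2% | 11% / 53% |
| 0.8 | 0.847 | 0.407 | 2.08 | 0.04% | 8.5% / 70% |

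The effect can instead be set at 0.889 SD of the within-person difference, which gives the simple paired test 80% power. The independent test then has 57%, 30% and 13% power at ρ = 0.5, 0.7 and 0.8, against 79% for the period-adjusted analysis. On this scale the raw effect, 0.889 × √(2(1−ρ)), shrinks from 0.89 to 0.69 to 0.56 SD, so part of that fall comes from the scaling. The table holds the raw effect fixed.

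**Reading 2: diets compared on changes (week 2 − week 0; week 5 − week 3).**
- Equal correlation between all visits: the two changes are uncorrelated. The independent test assumes 4(1−ρ) for the variance of a difference between changes, and the true value is also 4(1−ρ). The ratio is 1.00 and the type I error 5.0%.
- Exponential decay with a week 2 to week 5 correlation of 0.5: correlations at 1, 2, 3 and 5 weeks are 0.794, 0.630, 0.500 and 0.315. Each change has variance 2(1−0.630) = 0.740. Their covariance is 0.500 − 0.794 − 0.315 + 0.500 = −0.109. The assumed variance is 2 × 0.740 = 1.480; the true one is 1.480 + 2 × 0.109 = 1.698. The ratio is 0.87 and the type I error 6.6%. At 0.7 and 0.8 the ratios are 0.91 and 0.94, with type I errors of 6.0% and 5.6%.
- The test also uses 22 df where the 12 people supply 10 or 11.
- If nothing carries over past the washout, the change contrast is noisier than the end-value contrast: 4(1−ρ) against 2(1−ρ), or 2.0 times the variance, under equal correlation, and 1.70, 1.54 and 1.47 times under decay.

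**Reading 3: sequences compared on each person's period difference.** Here the two groups are different people, and the independent t-test (10 df) is the standard period-adjusted crossover test. Simulated data sets gave identical t statistics for the two analyses.

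**Sizing the next study** (illustrative 0.5 SD effect, 80% power, normal approximation). Crossover total: 2(1−ρ)(1.96+0.84)²/0.5², which is 63, 32 and 19 at ρ = 0, 0.5 and 0.7. The between-person SD alone gives 126 in total for a parallel trial and cannot size a crossover. Even with the right SD, 12 people fix it only loosely. The 95% limits for the required N, df/χ² at 0.975 and 0.025, run from 0.49 to 3.1 times the point value at 10 df and from 0.50 to 2.9 times at 11 df.

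**The case against.** The strongest reply is that the damaging reading is one of three. Aim 1 speaks of changes, and each diet has its own starting visit, so the between-group test may be meant for changes, where the error is slight. That is a fair reading of Aim 1. Aim 2 has no such wording, however, and the Statistical analysis paragraph chooses neither contrast.

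Several limits stand:
- The size depends on ρ, which the documents do not give. Below about 0.13 the independent interval is no wider, because its extra degrees of freedom offset the lost pairing. A clearly positive correlation is plausible for measures such as grip strength repeated in the same person three weeks apart, but it is an assumption.
- The documents do not say that the next study will be a crossover. A parallel-group study would need the between-person SD.
- If the paired test is meant to pair the two diets within a person, it would supply the missing SD. The plan does not say so.
- The looseness of the SD comes from having 12 people and remains after any change of test.
- A period term and an end-value contrast are choices, and the advantage of end values over changes depends on no carryover.

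On the end-value reading the error is conservative, in a pilot. That limits its seriousness but does not make the analysis fit the design.

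**Conclusion.** The concern holds as a conditional one. Read as diet against diet on end values, the planned test does not match the crossover. At assumed ρ of 0.5 to 0.8 its intervals are 1.3 to 2.1 times too wide, and it does not give the SD of the within-person diet difference. On changes the effect is small: type I error of 5.0% to 6.6% under the correlation patterns examined. Between sequences on period differences there is no error. The plan does not choose among these readings, which give materially different results. All sizes rest on the assumed correlations, equal SDs, six per sequence and no dropout. No participant is affected. The wording should be corrected because the stated purpose of the pilot depends on it.

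**What to change.** For each outcome, specify a paired, period-adjusted crossover analysis. Compute each participant's week 2 minus week 5 difference and compare these differences between the two sequences; half the difference between the sequence means is the diet effect. Report that effect with its 95% interval, the SD of the within-participant diet difference and the between-participant SD, each SD with confidence limits. Giving both SDs serves either a crossover or a parallel follow-on. How that study chooses its SD and target difference can be left to its own protocol. If the before-and-after paired tests within each diet are kept, label them as such, so that they are not taken for the diet comparison.

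The cost is SAP wording and a few lines of output, with no new visits or data. The period term uses one degree of freedom: 79% power against 80% for the simple paired test when there is no period effect. If changes are kept as the contrast and visits are equally correlated, moving from 22 to 10 df lowers power from 84% to 79%.
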